The baseline, 8-week, and 3-month visits will entail data collection using validated questionnaires and self-report paper forms at the CSRU. The eight week visit will take place between five to eleven weeks after enrollment. The three month visit will occur from 10 to 14 weeks after enrollment. At the 8-week visit participants will be asked to complete a qualitative interview in addition to the paper surveys. Responses will be recorded on a cell phone and we will use transcription plus LLC <https://www.transcriptionplus.net> transcription services. Participants will complete the forms themselves, and they will be entered into the OnCore system by the project manager. These forms will be kept in paper form in each study participant's record and will be kept in a locked file cabinet at the Yale Center for Clinical Investigation. Only the PI and project manager will have access to the participant's records. Forms will be coded with subject number; no personally identifiable information will be associated with these forms. Blood will be drawn by staff at the Church Street Research Unit and sent to the YCCI Core Lab for processing of the glucose, cholesterol, and triglyceride markers. The biomarker information will then be linked to our study on OnCore. The OnCore database will be supported by the Yale Center for Clinical Investigation/ CTSA. Incomplete or missing data prompts follow-up calls or electronic queries in OnCore. Our OnCore database will be checked for completeness in real-time from internal checks; while the PI and project manager will perform weekly audits for complete data.

The project manager will use a study cell phone for the purposes of recruitment, and reminder texts for participants. The project manager will make routine follow-up calls to remind study subjects of their appointments. Attrition will be minimized and data collection optimized with a relatively short intervention duration together with a \$150 individual participant remuneration. Payment will be made through the ONCORE bank of America gift card program with remuneration to be as follows. (\$50 dollars at baseline, \$50 dollars at eight week follow-up and \$50 dollars at three month follow-up) In [name] ongoing studies in fibromyalgia and Irritable Bowel Syndrome patients (n=108), he has achieved complete (no missing data) datasets based on robust data collection, retention, and follow-up procedures in collaboration with the YCCI.

Timeline.

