Feasibility outcomes will be observed, recorded, and qualitatively evaluated. Descriptive characteristics of the cohort will be summarized with means and standard deviations and counts and percentages according to intervention group. Although this pilot study will not be powered to test all outcomes for statistical significance, the primary quantitative outcomes are expected to have continuous Gaussian distributions making possible the comparison of intervention and control group results with linear mixed effects regression models that can accommodate the clustering of outcome results within couples. Finally, in anticipation of future studies of the metabolic syndrome outcome,

selected analyses will be conducted to compare the utility of the composite metabolic syndrome outcome and with a version of this outcome yielded by a measurement model in a structural equation modeling context.

Hypothesis 1: Self-reported physical health will be greater on average for participants in the MBSR intervention group compared to a wait-list control group. A multivariable linear mixed effects model will be used to assess whether self-reported physical health is greater in the intervention group than in the control group. A random effect will be used to account for the clustering of outcome values within couples. A pre-specified set of covariates will be entered into the regression model including baseline self-reported physical health and demographics and contextual factors that differ significantly across intervention and control groups. Model goodness of fit will be assessed with residual analysis, influence statistics, and goodness-of-fit statistics.

Hypothesis 2: MBSR will reduce each partner's self-reported stress and increase their mindfulness. The analyses for these two secondary outcomes will proceed according to the same procedures as cited for Hypothesis 1 above.

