How quantitative and qualitative data will be combined to understand outcomes. Qualitative data will be analyzed using Atlas.ti software and themes will be identified regarding partner influence on study experience. Key demographic characteristics and results from quantitative questions regarding decision making in participation and adherence will be entered into the software as coded attributes. Queries will be conducted to investigate the relationships between identified themes and coded attributes. Finally, the results of this qualitative analysis will be used to formulate hypotheses about the meanings and mechanisms underlying the quantitative results for Hypotheses 1 and 2, and especially, for the results of dyadic analyses of couple members' simultaneous engagement in the MBSR intervention.

Power: The sample size procedure in PASS shows that in anticipation of loss-to-follow-up, and with recognition of dependency in results from couples, the effective sample size is estimated to be 70, a reduction of 10 from the enrollment of 80 study participants. Assuming power of 80%, an outcome standard deviation of 10, and equal assignments to the intervention and control groups, this effective sample size will allow for detection of a difference between intervention and control groups mean values for the SF-12 outcome of 6.43 or more at the two-sided level of significance of 0.05. The sample size procedure in PASS was performed.

SECTION III: RECRUITMENT/CONSENT AND ASSENT PROCEDURES

1. Targeted Enrollment: Give the number of subjects: 80 participants

- a. Targeted for enrollment at Yale for this protocol: 80
- b. If this is a multi-site study, give the total number of subjects targeted across all sites: N/A

2. Indicate recruitment methods below. Attach copies of any recruitment materials that will be used.

- | | | |
|---|---|-------------------------------------|
|  Flyers |  Internet/Web Postings |  Radio |
|  Posters |  Mass E-mail Solicitation |  Telephone |
|  Letter |  Departmental/Center Website |  Television |
|  Medical Record Review* |  Departmental/Center Research Boards |  Newspaper |

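### The detectable SF-12 difference of 6.43 does not follow from its stated inputs, which give about 6.8 (t-test) or 6.7 (normal approximation)

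*Protocol*

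**What the plan says.** The Power paragraph (Protocol, Section I, item 13, Statistical Considerations) starts from the 80 people to be enrolled and discounts that number for loss to follow-up and for dependency within couples: "the effective sample size is estimated to be 70, a reduction of 10 from the enrollment of 80 study participants". It then lists its remaining inputs: "Assuming power of 80%, an outcome standard deviation of 10, and equal assignments to the intervention and control groups", with a two-sided significance level of 0.05. Its conclusion is that "this effective sample size will allow for detection of a difference between intervention and control groups mean values for the SF-12 outcome of 6.43". It names PASS as the software.

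The same item describes the Hypothesis 1 analysis as a linear mixed model with a random effect for couple. On covariates it says: "A pre-specified set of covariates will be entered into the regression model including baseline self-reported physical health". The power paragraph does not mention this adjustment.

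**The concern.** The paragraph ties 6.43 to an effective sample size of 70 and supplies everything else that a two-group comparison of means needs, so the figure can be checked without any outside assumption. It looked too small for 35 subjects per arm.

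This is the only power figure in the protocol, and it concerns the SF-12, which the Background (Aim 2) names as the primary outcome. The paragraph tells the reader that the discount from 80 to 70 has been applied. If the difference quoted is not the one that 70 supports, the trial appears more sensitive than its own assumptions allow.

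**Working it through.** **Inputs, all from the Power paragraph.** Effective total 70, so n = 35 per arm; SD = 10; power 80%; two-sided alpha 0.05; equal allocation.

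**Attempt to reproduce 6.43**

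The standard error of the difference is SD × √(2/n) = 10 × √(2/35) = 2.390.

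- *Normal approximation:* (1.960 + 0.8416) × 2.390 = **6.70** (6.697 unrounded).
- *Two-sample t-test, noncentral t with 68 df:* **6.79** (6.794).
- *Same standard error, degrees of freedom counted on couples (40 − 2 = 38):* **6.87**.

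None of these is 6.43. Other readings at a total of 70 fail as well: a one-sided 0.05 test gives 5.94 (normal) or 6.00 (t), and a 30/40 split gives 6.86 (t). Rounding cannot account for a gap of 6.697 − 6.43 = 0.27 or 6.794 − 6.43 = 0.36 in a figure given to two decimals.

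**Power at 6.43 with 35 per arm**

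- *Normal:* 6.43 / 2.390 − 1.960 = 0.730, and Φ(0.730) = **76.7%**.
- *t, 68 df:* **75.5%**.
- *t, 38 df:* **74.6%**.

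**Sample size at which 6.43 would be right**

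- *Normal:* n = 2 × [(1.960 + 0.8416) × 10 / 6.43]² = 37.97, so 38 per arm.
- *t-test:* 39 per arm.

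| Effective n per arm (total) | Normal | t-test |
|---|---|---|
| 35 (70) | 6.70 | 6.79 |
| 38 (76) | **6.43** | 6.51 |
| 39 (78) | 6.34 | **6.43** |
| 40 (80) | 6.27 | 6.34 |

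A further route to 6.43 is 40 per arm with 38 df, that is, 20 couples per arm with no loss and no within-couple correlation (6.4285). Three different calculations therefore reach the printed figure, so the match does not show which one was run. It shows only that 6.43 belongs to a larger sample than 70, or to an input that is not stated.

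**What unstated input would rescue 6.43 at 70**

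The SD would have to be 10 × 6.43/6.794 = 9.46 (t) or 10 × 6.43/6.697 = 9.60 (normal). If that reduction came from adjusting for baseline, the residual SD is SD × √(1 − r²). The baseline-outcome correlation would then be r = √(1 − 0.946²) = 0.32 (t) or √(1 − 0.960²) = 0.28 (normal).

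**The case against.** The strongest reply is that the planned Hypothesis 1 model adjusts for baseline self-reported physical health. A baseline-outcome correlation of only about 0.3 brings the detectable difference at 70 down to 6.43, so the power of the analysis actually planned may not be overstated at all. That is a fair statement about the trial, but it does not rescue the paragraph. The paragraph gives an SD of 10 for the outcome itself, not a residual SD, and states neither a correlation nor an R². If the credit was intended, an input is missing from the statement and the figure still does not follow from what is written.

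The second reply is that little depends on the number. The protocol describes a pilot that is not powered for every outcome; enrolment is fixed at 80; 6.43 is an output of that number and not a target that set it; and no threshold or stopping rule uses it. All of this stands, and it limits the weight of the point. It does not make the figure right.

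The protocol also does not break the reduction from 80 to 70 into a loss rate and a within-couple correlation. That is missing detail that a statistical analysis plan could supply, and nothing in the protocol shows 70 to be wrong. The check above takes 70 as given.

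**Conclusion.** The figure is wrong as written. On the stated inputs the detectable difference is 6.79 (t-test) or 6.70 (normal approximation), so 6.43 is too small by 0.36 or 0.27 points, about 4 to 6% of the stated figure. Equivalently, power for a difference of 6.43 is 75.5% or 76.7% instead of 80%.

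This rests on the protocol's own effective size of 70, SD of 10 and two-sided 0.05 level, applied to an unadjusted comparison of two means. It does not establish how 6.43 was obtained, and it does not claim that the baseline-adjusted analysis will fall short of 80% power. The error runs in the favourable direction, its practical effect is small, and it should be corrected.

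**What to change.** Check the PASS output for the inputs that were entered, then make the paragraph consistent in one of these ways:

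- replace 6.43 with about 6.8 (6.7 if a normal approximation is meant), keeping 80% power; or
- keep 6.43 and state power of about 76%; or
- if credit for baseline adjustment was intended, keep 6.43 and 80% power, and state the assumed baseline-outcome correlation (0.32 by t-test, 0.28 by normal approximation) with its basis.

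While the paragraph is being edited, it would help to add the loss rate and within-couple correlation behind the 70, but the correction does not depend on that.

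The cost is a rewording of one paragraph. Under the first two options the stated sensitivity becomes slightly less favourable. Enrolment, design and analysis stay as they are.
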